2.3 RISK/BENEFIT ASSESSMENT

2.3.1 KNOWN POTENTIAL RISKS

Hospital Discharge Study

This is a low-risk intervention. Since the intervention is already being conducted at the two sites by clinical pharmacists when there is administrative capacity to do so, we do not anticipate any additional risks involved with the hospital discharge intervention.

There is a small risk of breach of confidentiality with regards to the electronic health records data collected by the researchers at the end of the study; however, all data will be kept on password-protected, encrypted study site computers. Only investigators and study staff who are IRB-approved will have access to the study data. Since we are examining data at the end of the intervention, the data analysis is similar to a retrospective secondary data analysis.

To reduce the risk of COVID-19 exposure, some or all of the intervention activities (medication reconciliation, patient/caregiver education and counseling) will be conducted over the phone.

Focus Groups and Interviews

Individuals who participate in the focus groups and/or interviews may experience mild discomfort about certain questions. However, they will be reminded at the beginning of the focus group that they are not required to answer any questions they find cause discomfort and that they may stop the focus group/interview at any time.

There is also a small risk of breach of confidentiality. Interviewees/participants of focus groups/interviews will be given number identifiers, which will be kept separate from their identifiers/demographic information. Only the study staff will have access to the identifiers. This sub-study will not include any patient observation or use of PHI.

Observations will not affect any clinical decisions or clinical care. The pharmacist will be notified that observations will take place and that no identifiable information will be recorded about the interactions. Patients who may have interactions with the pharmacists will not be notified of the observations for research, since information will not be collected about them. Individuals who participate in the observations may experience mild discomfort when being observed. However, they will be reminded at the beginning of the observation that they are not required to participate in the observations and can stop the observation at any time. There is also a small risk of breach of confidentiality. Participants in the observations will be given number identifiers, which will be kept separate from their identifiers/demographic information. Only the study staff will have access to the identifiers.

Time and Motion Study/Cost-Effectiveness Analysis

There is a small risk of breach of confidentiality. Patients will be assigned a unique identifier within the TimeCaT application so that no PHI is transmitted over the internet. Only study staff will have access to the identifier and linking file, which will be stored separately on Box and will only be accessed on a password protected, encrypted study site computer. When not in use, iPads will be stored in a locked cabinet behind a locked office door in the Department of Medicine's administrative office at each site.

Observations will not affect any clinical decisions or clinical care. The pharmacist will be notified that observations will take place. Patients who may have interactions with the pharmacists will be told that this is part of an ongoing study examining pharmacist activities. Individuals who participate in the observations may experience mild discomfort when being observed. However, they will be reminded at the beginning of the observation that they are not required to participate in the observations and can stop the observation at any time.

There is also a small risk of breach of confidentiality with regards to the electronic health records data collected by the researchers at the end of the study; however, all data will be kept on password-protected, encrypted study site computers. Only investigators and study staff who are IRB-approved will have access to the study data. Since we are examining data after the end of the study period at both sites, the data analysis is similar to a retrospective secondary data analysis. We will exclude data for patients who have opted out of research studies from data extracts.

2.3.2 KNOWN POTENTIAL BENEFITS

Individuals may receive consultations with pharmacists that help them understand their medications and/or chronic conditions more thoroughly.

3 OBJECTIVES AND ENDPOINTS

Primary Outcome

We chose an endpoint of 30-day post-discharge utilization as our primary outcome because the RE-AIM model points to the importance of institutional-level effectiveness and cost. We chose to power this trial on an absolute utilization reduction of 2.5% (% of patients with readmissions or ED visits within 30 days of hospital discharge) from a baseline of 27.5%.

We define this utilization in two different ways, based on what data is available. For the first analysis, we will use same-hospital utilization data. Both site PIs can electronically access inpatient admission, observation stay, and ED visit data for their health system. These three utilization types will represent the basis for the first RCT analysis (*manuscript #2 above*).

We recognize the limitations of same-hospital utilization data.^{xxx} As such, the RCT is powered on a primary endpoint of same-state 30-day hospital readmissions and ED visits (manuscript #6 above).

This utilization will be tracked with data from the Massachusetts All Payer Claims Data (APCD) database and California's Office of Statewide Health Planning and Development.^{xxxi} Because we expect little utilization in other states (discharge to another state is an exclusion criterion) and because we do not anticipate any differential effect on such utilization, we will not track it. Statewide data sources do not track observation stays, so they will be excluded from statewide analyses. However, we will conduct a sensitivity analysis projecting changes in same-hospital observation stays to the statewide analysis.

The current version of this protocol does not include information for these analyses using other data sources; we will include this information in subsequent versions through protocol/IRB amendments.

Secondary Outcomes

We will examine the endpoints in the following subgroups:

Patients:

- 1) Patient socioeconomic status (estimated via median income of home census tract);
- 2) Patient medication adherence and literacy (as assessed by study pharmacists, in addition to using limited English proficiency as a proxy for low medication literacy);
- 3) Study site;
- 4) Ten or more medications;
- 5) Three or more high risk medications;
- 6) Patient history of congestive heart failure;
- 7) By receipt of different intervention components;
- 8) Patient age groups;
- 9) Before and after historical changes to the intervention and control arms;
- 10) Primary outcome restriction to medication-related post-discharge utilization;
- 11) Primary outcome restriction to 7-day post-discharge utilization;
- 12) 30-day mortality
- 13) Effect of the intervention on each type of utilization considered separately (ED visits alone, observations stays alone, readmissions alone)

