1 PROTOCOL SUMMARY

1.1 SYNOPSIS

Title:

PHARMacist Discharge Care (PHARM-DC)

Study Description:

To implement evidence-based pharmacist-led strategies for preventing ADEs after hospitalization, use implementation science methodology to study implementation at two large medical centers, and examine the cost-effectiveness of the intervention.

There are three components to this study: (1) the prospective, randomized trial, which includes a pharmacist-led hospital discharge care intervention, (2) the qualitative study, which involves focus groups and interviews, and (3) a cost-effectiveness study, which involves a review of the literature and a time-and-motion study component.

Objectives:

- (1) *Pharmacist-led Hospital Discharge Care Intervention:* To test the effect of **PHARMacist Discharge Care (PHARM-DC)** Toolkit on post-discharge utilization among patients most at risk for post-discharge adverse drug events (ADEs): recently discharged older adults taking ≥ 10 chronic prescription medications or ≥ 3 high-risk medications.
- (2) *Qualitative study:* To study barriers and facilitators of implementing PHARM-DC at two sites, Cedars-Sinai Medical Center (CSMC) and Brigham and Women's Hospital (BWH) using a qualitative study.

(3) **Cost-Effectiveness Study:** To analyze the costs of PHARM-DC, including the incremental cost per readmission averted and the net incremental cost from the health system perspective using a time-and-motion study and cost-effectiveness analysis.

Endpoints: *Pharmacist-led Hospital Discharge Care Intervention:*
Primary Endpoint: 30-day post-discharge utilization, including same-hospital utilization data and same-state 30-day hospital readmissions and ED visits.

Secondary Endpoints: To assess the *Reach* of the intervention, we will examine differences in effectiveness across sites, and for patients of different ages, sex, taking different numbers of medications, with different comorbidities/diagnoses, and living in zip codes reflecting different median incomes.

Study Population: The study population includes individuals being discharged from the hospital at high risk for adverse drug events. Inclusion criteria includes individuals being discharged from a medical/surgical ward and either being 55 years of age or older and having 10 or more chronic prescription medications, **or** using three or more high-risk medications before or during hospitalization.

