8 STATISTICAL CONSIDERATIONS

8.1 STATISTICAL HYPOTHESES

Hypothesis 1: PHARM-DC will reduce post-discharge utilization reduction of 2.5% (% of patients with readmissions or ED visits within 30 days of hospital discharge) from a baseline of 27.5%.

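### The primary endpoint is stated inconsistently: the version the trial is powered on is not the version the analysis section defines, and the single 0.05 test names neither

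*Combined protocol and SAP*

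**What the plan says.** Five places in the combined protocol and SAP bear on which outcome decides the trial.

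- **Section 1.1 (Synopsis).** The primary endpoint is "30-day post-discharge utilization, including same-hospital utilization data and same-state 30-day hospital readmissions and ED visits". Both versions appear in one sentence with no order between them.
- **Section 3 (Primary Outcome).** "We define this utilization in two different ways, based on what data is available". The same-hospital version comes first: "For the first analysis, we will use same-hospital utilization data", built from inpatient admissions, observation stays and ED visits. The section then acknowledges the limits of same-hospital data and says "the RCT is powered on a primary endpoint of same-state 30-day hospital readmissions and ED visits". For that version, "Statewide data sources do not track observation stays, so they will be excluded from statewide analyses". It also says "The current version of this protocol does not include information for these analyses using other data sources" and promises the missing text by amendment.
- **Section 8.1.** "PHARM-DC will reduce post-discharge utilization reduction of 2.5% (% of patients with readmissions or ED visits within 30 days of hospital discharge"). Observation stays are not mentioned and no data source is named.
- **Section 8.2.** A two-sided 0.05 Z test is the primary analysis, with 4,888 per group to detect 27.5% versus 25.01%. No data source is named.
- **Section 8.4.1.** The Z test is again primary. Utilization is defined as ED visits, observation stays and inpatient readmissions, with planned readmissions removed by the CMS algorithm. No data source is named.

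**The concern.** A confirmatory trial needs one outcome that decides it. Here the version that carries the power calculation has no operational definition in the analysis section. The version defined there includes a component that, by section 3's own account, the statewide data do not hold.

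Three things follow.

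1. Applying section 8.4.1 literally tests a different endpoint from the one that was powered.
2. If the same-hospital and same-state results disagree, nothing written says which is the trial's result. The same-hospital result arrives first, so the choice could be made after seeing data.
3. The 80% power belongs to the same-state version. No power is given for the analysis reported first, so a negative first result cannot be read against that figure.

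The plan does not say that success on either version would be claimed. If it were, the type I error would exceed 5%.

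**Working it through.** **Side by side**

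| Place | Data source | Observation stays | Role given |
|---|---|---|---|
| 1.1 | both | not stated | primary (both) |
| 3, first analysis | same hospital | included | analysed first |
| 3, powered endpoint | same state | excluded | a primary endpoint; powered |
| 8.1 | not named | not mentioned | hypothesis |
| 8.2 | not named | not mentioned | primary Z test, power |
| 8.4.1 | not named | included | primary Z test, definition |

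No section gives a testing order, an alpha split or a rule for discordant results.

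**Step 1: the plan's own figure.** Inputs from section 8.2: p1 = 0.275, p2 = 0.2501, n = 4,888 per arm, two-sided 0.05. Pooled-variance Z test:

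- SE0 = √[2 × 0.26255 × 0.73745 / 4,888] = 0.008901
- SE1 = √[(0.275 × 0.725 + 0.2501 × 0.7499) / 4,888] = 0.008897
- Power = Φ[(0.0249 − 1.96 × 0.008901) / 0.008897] = Φ(0.838) = 79.9%

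The same formula solved for 80% power gives 4,901 per arm, 0.3% from the stated 4,888. The arithmetic is sound, and by section 3 it belongs to the same-state version.

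**Step 2: what power the same-hospital version might have (illustration).** The documents do not give the inputs. Assume that a share c of same-state events is captured at the study hospital, and that a share o of patients have an observation stay as their only event. The same-hospital rate is then c × (27.5%, 25.01%) + o. The range c = 0.80–0.95 is an assumption. Section 8.4.4 uses a figure of at least 80%, but for costing, and section 3's health-system access may capture more. The range o = 0–4% is also an assumption.

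Example, c = 0.80 and o = 0: 22.0% versus 20.008%, difference 0.01992, SE0 = 0.008240, SE1 = 0.008237. Power = Φ(0.458) = 67.6%.

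| c | o = 0 | o = 2% / 4%, same relative reduction | o = 2% / 4%, no effect on them |
|---|---|---|---|
| 0.80 | 67.6% | 72.5 / 76.9% | 64.8 / 62.3% |
| 0.85 | 71.0% | 75.5 / 79.7% | 68.4 / 66.1% |
| 0.90 | 74.2% | 78.4 / 82.2% | 71.8 / 69.8% |
| 0.95 | 77.1% | 81.1 / 84.6% | 75.1 / 73.2% |

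The overall range is 62.3–84.6%, on both sides of 80%.

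**Step 3: how often the versions would disagree (illustration).** Let S be the same-state rate and H = cS + o. Assume that observation-only patients have no same-state event, so the joint rate is cS. The correlation of the two test statistics is ρ = (cS − SH) / √[S(1−S)H(1−H)]. With S = 0.275, c = 0.80 and o = 0, ρ = (0.22 − 0.0605) / √(0.199375 × 0.1716) = 0.86.

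Under the planned effect, with rates averaged over arms, the chance that exactly one version is significant in favour of the intervention is:

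- o = 0: 16.9%, 10.1% and 6.5% at c = 0.80, 0.90 and 0.95.
- o = 2–4%, same relative reduction: 16.4% (at both o = 2% and 4%), 11.2–12.5% and 9.0–11.1%.
- o = 2–4%, no effect on these patients: 20.7–23.9%, 13.9–16.9% and 10.6–13.7%.

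**Step 4: type I error if success on either version were claimed (illustration).** Bivariate normal with the ρ above and S = 0.275:

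| c | o = 0 | o = 2% | o = 4% |
|---|---|---|---|
| 0.80 | 7.4% | 7.8% | 8.1% |
| 0.90 | 6.7% | 7.2% | 7.6% |
| 0.95 | 6.2% | 6.9% | 7.3% |

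**The case against.** The best reply is that section 3 already settles the matter. It attaches the words for a primary endpoint only to the same-state version, gives a reason, and powers the trial on it. Sections 8.1 and 8.2 use the same 27.5% baseline, and section 8.1 lists the same components. Section 8.4.1 matches the same-hospital components exactly, so it can be read as the definition for the first analysis, with the statewide text openly deferred. On this view the fault is a missing label.

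Much of this is fair as a reading of intent, and same-state is the natural default. It does not remove the conflict. The synopsis still names both versions as primary. Section 8.4.1 sits beside the primary Z test without a same-hospital label, although section 8.4.7 shows that the authors label the source when they mean to. Section 3 does add that "we will conduct a sensitivity analysis projecting changes in same-hospital observation stays to the statewide analysis". That partly bridges the two definitions but does not say which one decides.

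A second reply is that every figure except 79.9% rests on assumed inputs, and that two overlapping definitions will sometimes disagree even after the text is aligned. Both statements are correct. The figures show only that the choice of version is not a formality. The defect rests on the text. What alignment changes is that the meaning of a disagreement is settled in advance.

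**Conclusion.** The concern holds, and the text should be corrected before outcomes are compared by arm. Section 3, the synopsis and section 8.4.1 do not name the same primary endpoint, and the primary test does not say which it uses. The sample size is not in error: 4,888 per arm gives 79.9% power for the same-state version.

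The consequences of leaving the choice open depend on capture and observation-only shares that the documents do not report. Over 80–95% capture and 0–4% observation-only patients, same-hospital power is about 62–85%, and the versions disagree in about 6.5–24% of trials under the planned effect. An either-version claim, which the plan does not make, would carry a type I error of about 6.2–8.1% (6.2–7.4% with no observation-only patients).

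**What to change.** Before outcomes are compared by arm:

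1. Name one primary endpoint in the same words in sections 1.1, 3, 8.1 and 8.4.1. On section 3's powering statement, this is same-state 30-day readmission or ED visit without observation stays. Label the same-hospital analysis with observation stays as supportive, with no separate confirmatory claim at 0.05. State in sections 8.2 and 8.4.1 that the primary Z test applies to the same-state endpoint.
2. State in section 8.2 that the 80% power refers to the same-state endpoint and that power for the same-hospital analysis was not calculated.
3. When adding the statewide analysis text that section 3 already promises, confirm that the planned-readmission rule of section 8.4.1 applies to the statewide data.

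The cost is aligned wording in five sections and one confirming sentence in the promised text. No further patients are needed, and no data source beyond those section 3 names. The statewide analysis text has still to be written, but the plan already commits to it. The real downside is that the first, same-hospital manuscript cannot be presented as the primary result, which must wait for the statewide data.

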1.3 SCHEDULE OF ACTIVITIES (SOA)

(1) *Pharmacist-led Hospital Discharge Care Intervention:*

- a. Eligible pharmacists at each study site will be selected to participate in the intervention based on their training in transitions of care.
- b. Using a daily Epic report generated by EIS, a coordinator at each site will identify eligible patients and notify pharmacists. Trial enrollment will occur for eligible patients admitted every day prior from Monday to Friday.
- c. Randomization will be performed via the REDCap (Research Electronic Data Capture) system.
- d. All eligible patients (both arms) will receive the Best Possible Medication History (BPMH)
- e. Patients in the Study arm:
 - i. On hospital day 1, or as soon as possible: Receive an Initial Medication Regimen Assessment. Clinical pharmacists assess regimen appropriateness, assess barriers to medication adherence, start filling out the Actions for Assessing Adherence Barriers worksheet
 - ii. On hospital day 1, or as soon as possible: Receive a Pre-Discharge Intervention, which, depending on the patient condition, might include a: trial to discontinue certain medications during the hospital; discussion of side effects, flags for new medications prescribed, education about critical barriers to adherence.
 - iii. On day of discharge: Receive an At-Discharge Intervention, which may include a brief discussion of medication changes, discussion of side effects, discussion of red flags for new medications. Clinical pharmacists will also consult with inpatient clinicians and pharmacists to discuss the medication list and will ensure that the e-prescribing is done appropriately.
 - iv. 1-3 days after discharge: Receive a Post-Discharge Intervention, which includes a call with a patient to discuss the patient's regimen, discussion of side effects, red flags of new medications, a motivational interview, a discussion of barriers to adherence. Other tasks might include a phone call with the patient's primary care physician.
 - v. After initial phone call: Some patients, depending on need, might receive a second phone call if needed, a video visit, clinic visit with pharmacist, embedded mental health.
 - vi. For any of the above-mentioned activities, patients may be contacted by pharmacists over the phone instead of in-person to reduce COVID-19 exposure to patients, caregivers, and pharmacists.
- f. Patients in the Control arm:

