6 STUDY INTERVENTION

6.1 STUDY INTERVENTION(S) ADMINISTRATION

6.1.1 STUDY INTERVENTION DESCRIPTION

PHARM-DC Intervention Overview

Pharmacists at both study sites have experience in providing discharge counseling and in making post-discharge phone calls. This experience will ensure that PHARM-DC is being tested in its best light. The Toolkit content and 1-2 hours of introductory training add three major components:

1. Rather than incorporating content based solely upon their prior training and experience, pharmacists will use the *PHARM-DC Toolkit*, which *summarizes the evidence* for post-discharge medication management.
2. Pharmacists will *assess patient needs* and *customize accordingly*. All patients will receive one discharge counseling visit and one post-discharge phone call, but pharmacists will find that some patients need further phone calls, interventions, referrals, or other interactions.
3. Although pharmacists have long been successful in leading med rec interventions, most work focused on *what medications patients had been prescribed and are taking*. This is a necessary step, but we believe most benefit occurs from the subsequent step of figuring out what medications patients *should be taking*.

PHARM-DC toolkit:

- 1) Pharmacist review of discharge med rec and medication appropriateness (e.g., reduction in polypharmacy);
- 2) In-hospital room visit to screen for previous barriers to safe medication use, initiate management of these barriers, and communicate with post-discharge providers regarding likely actions that will need to be taken;
- 3) Post-discharge phone call by a pharmacist 1-3 days after discharge to screen for patient/caregiver lack of understanding of their medication regimen, medication non-adherence, early side-effects, lack of knowledge of what ADEs to watch for and what to do if they occur, other barriers to safe medication use, and management of these problems;

4) Based on this risk assessment, pharmacists will tailor the interventions to each patient. The personalized intervention may include:

- a. **Patient education, counseling, and coaching** regarding the importance of taking medication as prescribed and contacting a designated caregiver or provider if there are problems;
- b. **Taking further steps to improve medication appropriateness;**

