- c. **Post-discharge assistance with obtaining medications**, including drug assistance programs (for reduced pricing) and linkage with community or social service organizations;
- d. **Pharmacist communication with key inpatient and outpatient providers** (e.g., PCPs; skilled nursing facilities; inpatient rehabilitation hospitals, including the California Rehabilitation Institute) to ensure that they understand changes to their patient's discharge medication regimen, including why those changes were made and recommended actions to take. This includes requesting Medication Administration Records (MAR) from downstream providers to facilitate this type of communication;
- e. **Communication with each patient's pharmacy** to ensure the pharmacy has an updated medication list, with focus on newly discontinued medications, and to encourage patient education as needed when patients fill their prescriptions;
- f. **Use of illustrated pill cards, pillboxes (traditional and electronic), and other tools** to help patients with low literacy better understand and adhere to their medication regimens;
- g. **Health information technology such as patient portals and texting** chatbots to facilitate communication between patients, pharmacists, and other providers after discharge;
- h. **Home pharmacist visits for high-risk patients** to educate them and to identify and manage challenges to safe medication use.

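### Secondary item 7 estimates effects by intervention components received, but receipt is set after randomization and partly by need, so these estimates are confounded in a direction that varies by component

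*Combined protocol and SAP*

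**What the plan says.** Section 3, Secondary Outcomes, opens its list with "We will examine the endpoints in the following subgroups". Item 7 is "By receipt of different intervention components", placed alongside study site, age group and heart failure history. It is therefore an analysis of outcomes and not a report of fidelity.

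Other sections say how components are allocated:

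- Section 6.1.1 gives every intervention patient one counseling visit and one call, then adds that "pharmacists will find that some patients need further phone calls, interventions, referrals, or other interactions".
- Section 6.1.1, item 4: "Based on this risk assessment, pharmacists will tailor the interventions to each patient". Item 4h is "Home pharmacist visits for high-risk patients".
- Section 1.3, item e.v, which follows the first call: "Some patients, depending on need, might receive a second phone call if needed, a video visit, clinic visit with pharmacist, embedded mental health".
- Section 6.1.1, item 3, times the core contact: "Post-discharge phone call by a pharmacist 1-3 days after discharge". That lies inside the 30-day outcome window.

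Control patients receive usual care, which can include a pharmacist consultation or call where clinically necessary (Section 1.3, item f). Section 8.4.2 plans logistic regression for the factors it names. Component receipt is not among them, and no comparator, time origin or adjustment is given for item 7. Its only caution is that the analyses it describes are underpowered and best used to shape hypotheses.

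**The concern.** Most of the patient subgroups in the list, such as site or age, are fixed at baseline, so randomization holds within them. Component receipt is not fixed at baseline. It arises after allocation, in the intervention arm, through two selection processes:

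1. **Need.** The extras go to patients judged to need them or to be at high risk. If need predicts return to hospital, those who get extras start at higher risk and those who get only the basic package start at lower risk.
2. **Availability.** A patient generally receives a call or later contact only if still event-free and reachable at that time. This selects recipients for good outcomes.

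Neither process has a counterpart in the control arm. Controls are not put through the toolkit's tailoring step, and any who receive a consultation or call were themselves chosen by clinical need. The caution in Section 8.4.2 concerns power; a larger sample would not remove this bias. Putting a null or adverse result for an intensive component down to low power would misread it.

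**Working it through.** **The plan's own figure.** For 27.5% against 25.01%, two-sided 0.05, 80% power, pooled variance (mean proportion 0.26255):

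n = [1.960·√(2·0.26255·0.73745) + 0.842·√(0.275·0.725 + 0.2501·0.7499)]² / 0.0249² = 4,901 per arm.

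Section 8.2 states 4,888, a difference of 0.3%; power at 4,888 is 79.9%. The figure reproduces, and about 2.5 points is the yardstick below. The documents give no figure for item 7.

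**Step 1: need only, no true effect.** From Section 8.2: 27.5% risk, applied to both arms. Assumed, because the documents do not give them: the share q of intervention patients receiving extras and their risk e. Each subgroup is compared with the whole control arm (also an assumption). The basic-only risk is then b = (0.275 - q·e)/(1 - q).

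- q = 20%, e = 37.5%: b = (0.275 - 0.075)/0.8 = 25.0%. Differences from control: +10.0 and -2.5 points. The chance that the basic-only contrast reaches p<0.05 is 75%.
- q = 20%, e = 30%: b = (0.275 - 0.060)/0.8 = 26.9%. Differences: +2.5 and -0.6 points.
- Over q from 10% to 40% and risk ratios (extras to basic) from 1.1 to 2.0, extras look 1.6 to 22.5 points worse and basic-only 0.3 to 7.9 points better. At a ratio of 1.0 there is no spurious effect.

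**Step 2: add event-free time.** Suppose the extra is given on day t, only to patients event-free until then, with constant hazard. Those with an earlier event count as basic-only. With hazard h = -ln(1 - e)/30 and s = exp(-h·t), the risk among recipients is 1 - exp(-h·(30 - t)), and the basic-only risk is [(1 - q)·b + q·(1 - s)]/(1 - q·s). With q = 20%:

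| Risk ratio | Day of extra | Extras (vs 27.5%) | Basic-only (vs 27.5%) |
|---|---|---|---|
| 1.25 | no requirement | 32.7% (+5.2) | 26.2% (-1.3) |
| 1.25 | 7 | 26.2% (-1.3) | 27.8% (+0.3) |
| 1.5 | no requirement | 37.5% (+10.0) | 25.0% (-2.5) |
| 1.5 | 7 | 30.3% (+2.8) | 26.9% (-0.6) |
| 1.5 | 10 | 26.9% (-0.6) | 27.6% (+0.1) |

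For extras to look worse than control, the 30-day risk of the patients selected for them must exceed 30.0% (contact on day 3), 34.3% (day 7) or 38.3% (day 10).

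**Step 3: the core call.** Section 8.2 assumes 7.5% unreachable or refusing. Put the call on day 2, with no effect and equal underlying risk. The hazard is -ln(0.725)/30 = 0.01072 per day. Recipients' risk is 1 - exp(-0.01072·28) = 25.9%. The share called is 0.925·exp(-0.01072·2) = 0.905. The risk in the rest is (0.275 - 0.905·0.259)/0.095 = 42.5% (computed unrounded). Here the bias favors receipt.

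**The case against.** The strongest reply is that item 7 is one short line in a list of 13, with no ordering of components, comparator or model. It could refer to the scheduled elements meant for every intervention patient, where non-receipt reflects reachability or discharge timing and not escalation. Only home visits are tied explicitly to high risk; other tailored items answer barriers such as literacy or cost, which the documents do not link to 30-day utilization. The 20% share and the subgroup risks are assumptions. The plan could also adjust for Appendix A covariates.

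Much of this stands as a limit on how far the point goes, and several stronger readings fail:

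- A reader might infer a planned dose-response analysis. The plan does not call it that or rank the components.
- A reader might infer that intensive components are bound to look harmful and basic delivery beneficial. Steps 2 and 3 show that the sign depends on the component, its timing and the strength of the link between need and risk.
- A reader might infer that this is the only planned look at components. Section 8.3 defines datasets by receipt of the in-hospital intervention and the call, and Section 8.4.7 addresses admission medication reconciliation.
- A reader might infer that hospitals would set funding by this analysis. The outputs for decision makers in Section 8.4.4 are not broken down by component.

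The core objection to item 7 survives. If only scheduled elements are meant, receipt is still post-randomization and biased, as Step 3 shows. Adjustment is not specified for item 7, and baseline covariates would not remove selection on being event-free at the time of contact.

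**Conclusion.** The point holds in this form: effect estimates by component receipt are confounded even with no true effect, because receipt is post-randomization and, for the tailored extras, driven by need or risk. Under the stated assumptions the spurious basic-only benefit can equal the 2.5 points the trial is powered on, with extras 10.0 points worse than control. Under milder assumptions it is 0.6 and 2.5 points, and event-free time can shrink or reverse the pattern. The sizes rest on assumed shares and risks, a crude comparison with all controls and, in Steps 2 and 3, constant hazard. That receipt is not randomized rests on the documents alone.

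A reader might also fear for the main result. The randomized primary comparison of all patients does not use component receipt and is unaffected. This is a cheap improvement to a secondary analysis.

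**What to change.** Remove item 7 from the effect subgroups in Section 3. Report component receipt as a description of delivery, using the Epic reports already planned in Section 6.3, without effect estimates.

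If the effect by likely intensity is of interest, compare the randomized arms within subgroups defined by baseline predictors of escalation. Appendix A already lists medication count before admission, comorbidity index and hospital admissions in the preceding three years. The discharge medication count, also listed there, should not be used, because the intervention can change it.

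Comparing calendar periods under item 9 is not a ready substitute. Nothing in the documents says that those changes switched a component on or off, and item 9 covers changes to the control arm too.

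The cost is a wording change and no new data. What is given up is a direct per-component effect estimate, which receipt-based subgroups could not validly provide.
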